AE = adverse event, BP = blood pressure, ECG = electrocardiogram, HR = heart rate, SAE = serious adverse event.

NOTES:

1. Triplicate 12-lead ECGs will be obtained at least 5 minutes apart within 1 hour before the start of infusion (pre-dose) on Day 1. Single ECGs will be obtained at 0.5, 1, 1.5, 2, 3, 4, 6, and 12 hours after the start of infusion on Day 1 and Day 15, within 1 hour before the start of the morning infusion on Days 2, 3, 4, 5, 6, 7, 8, 9, 10, 11, 12, 13, and 14, and in the morning on Day 16.
2. Vital signs will be measured within 1 hour before the start of infusion (pre-dose) and at 0.5, 1, 1.5, 2, 3, 4, 6, and 12 hours after the start of infusion on Days 1 and 15, within 1 hour before the start of the morning infusion and on Days 2, 3, 4, 5, 6, 7, 8, 9, 10, 11, 12, 13, and 14, and in the morning on Day 16.
3. An aliquot of the urine sample will be collected for neutrophil gelatinase-associated lipocalin (NGAL) and kidney injury molecule 1 (KIM-1). These samples may be analyzed after the end of the study if a clinical signal is detected. Instructions for collection and storage of these urine samples are included in the Study Reference Manual. Hematology assessments on Days 5 and 15 will also include total iron, total iron binding capacity, ferritin, haptoglobin, ceruloplasmin and reticulocytes. The albumin to creatinine ratio will be determined using the first morning void urine on Days 5 and 15. Urinalysis assessments before dosing on Day 15 will also include urine color.
4. GSK3342830 or placebo will be administered as a single IV infusion in the morning on Day 1, TID IV infusions (approximately every 8 hours) on Days 2, 3, 4, 5, 6, 7, 8, 9, 10, 11, 12, 13, and 14, and as a single IV infusion in the morning on Day 15. The planned infusion duration time is 1 hour.

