**Time and Events Table: Part 2 - Repeat Dose Escalation**

Procedure	Study Day															
	1	2	3	4	5	6	7	8	9	10	11	12	13	14	15	16
Randomization	X															
12-lead ECG 	X	X	X	X	X	X	X	X	X	X	X	X	X	X	X	X
Vital signs (BP, HR, oral temperature, respiration rate) 	X	X	X	X	X	X	X	X	X	X	X	X	X	X	X	X
Fasting clinical chemistry, hematology, and urinalysis tests 		X			X					X					X	
Treatment administration 	X	X	X	X	X	X	X	X	X	X	X	X	X	X	X	X
Blood collection for pharmacokinetics 	X		X			X			X			X	X		X	
Urine collection for pharmacokinetics 	X	X													X	X
Continuous cardiac monitoring 	X←Continuous review→															
AE review	X←-----Continuous review----->															
SAE review	X←-----Continuous review----->															
Concomitant medication review	X←-----Continuous review----->															
Discharge from inpatient unit 																X

AE = adverse event, BP = blood pressure, ECG = electrocardiogram, HR = heart rate, SAE = serious adverse event.

NOTES:

1. Triplicate 12-lead ECGs will be obtained at least 5 minutes apart within 1 hour before the start of infusion (pre-dose) on Day 1. Single ECGs will be obtained at 0.5, 1, 1.5, 2, 3, 4, 6, and 12 hours after the start of infusion on Day 1 and Day 15, within 1 hour before the start of the morning infusion on Days 2, 3, 4, 5, 6, 7, 8, 9, 10, 11, 12, 13, and 14, and in the morning on Day 16.
2. Vital signs will be measured within 1 hour before the start of infusion (pre-dose) and at 0.5, 1, 1.5, 2, 3, 4, 6, and 12 hours after the start of infusion on Days 1 and 15, within 1 hour before the start of the morning infusion and on Days 2, 3, 4, 5, 6, 7, 8, 9, 10, 11, 12, 13, and 14, and in the morning on Day 16.
3. An aliquot of the urine sample will be collected for neutrophil gelatinase-associated lipocalin (NGAL) and kidney injury molecule 1 (KIM-1). These samples may be analyzed after the end of the study if a clinical signal is detected. Instructions for collection and storage of these urine samples are included in the Study Reference Manual. Hematology assessments on Days 5 and 15 will also include total iron, total iron binding capacity, ferritin, and reticulocytes. The albumin to creatinine ratio will be determined using the first morning void urine on Days 5 and 15.

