### 10.3.2. Baseline Definition & Derivations

#### 10.3.2.1. Baseline Definitions

For all endpoints (except as noted in baseline definitions) the baseline value will be the latest pre-dose assessment.

Parameter	Study Assessments Considered As Baseline			Baseline Used in Data Display
	Screening	Day -1	Day 1 (Pre-Dose)	
Safety				
Hematology	X	X		Day -1
Clinical Chemistry	X	X		Day -1
12 Lead ECG	X	X	X	Day 1 (Pre-dose)
Vital Signs	X	X	X	Day 1 (Pre-dose)

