<=30	xx (xx%)	xx (xx%)	xx (xx%)	xx (xx%)
>30-<=59	xx (xx%)	xx (xx%)	xx (xx%)	xx (xx%)
>=60	xx (xx%)	xx (xx%)	xx (xx%)	xx (xx%)
QTcF (msec)				
n	xx	xx	xx	xx
<=30	xx (xx%)	xx (xx%)	xx (xx%)	xx (xx%)
>30-<=59	xx (xx%)	xx (xx%)	xx (xx%)	xx (xx%)
>=60	xx (xx%)	xx (xx%)	xx (xx%)	xx (xx%)

*Note to Programmer: Continue for all treatments in Part 1, Part 2, and Part 3. Present Part 2 and Part 3 on separate pages.*

Note: Baseline is defined as the last nonmissing measurement before dosing for the respective treatment period.  
Unscheduled measurements are not included in this summary table except when calculating baseline.

GlaxoSmithKline  
 Example : VS1  
 Protocol : 204847  
 Population : Safety

Table 2.16  
 Summary of Vital Signs

Study Part: 1

Vital Sign	Group	N	Planned Relative Time	n	Mean	SD	Median	Min.	Max.
XXXXXXXX (XXX)	GSK3342830 250 mg	XXX	Baseline	xx	xx.x	xx.xx	xx	xx	xx
			Day 1 - 0.5 HR	xx	xx.x	xx.xx	xx	xx	xx
			...						
			Follow-Up	xx	xx.x	xx.xx	xx	xx	xx
XXXXXXXX (XXX)	GSK3342830 500 mg	XXX	Baseline	xx	xx.x	xx.xx	xx	xx	xx
			...						
XXXXXXXX (XXX)	...	XXX	Baseline	xx	xx.x	xx.xx	xx	xx	xx
			...						

*Note to Programmer: Continue for all treatments in Part 1, Part 2, and Part 3. Present Part 2 and Part 3 on separate pages. Timepoints for Part 1 and Part 3 are Baseline, Day 1 - 0.5 HR, Day 1 - 1 HR, Day 1 - 1.5 HR, Day 1 - 2 HR, Day 1 - 3 HR, Day 1 - 4 HR, Day 1 - 6 HR, Day 1 - 12 HR, Day 2, Day 3, Follow-Up. Timepoints for Part 2 are Baseline, Day 1 - 0.5 HR, Day 1 - 1 HR, Day 1 - 1.5 HR, Day 1 - 2 HR, Day 1 - 3 HR, Day 1 - 4 HR, Day 1 - 6 HR, Day 1 - 12 HR, Day 2 through Day 14, Day 15 - 0.5 HR, Day 15 - 1 HR, Day 15 - 1.5 HR, Day 15 - 2 HR, Day 15 - 3 HR, Day 15 - 4 HR, Day 15 - 6 HR, Day 15 - 12 HR, Day 16, and Follow-Up. Vital sign measurements summarized are: Systolic Blood Pressure (mmHg), Diastolic Blood Pressure (mmHg), Oral Temperature (C), and Pulse Rate (beats per min).*

Note: Baseline is defined as the last nonmissing measurement before dosing.  
 Unscheduled measurements are not included in this summary table except when calculating baseline.

GlaxoSmithKline  
Example : VS1  
Protocol : 204847  
Population : Safety

Page 1 of n

Table 2.17  
Summary of Change from Baseline in Vital Signs

Note to programmer: Please use the shell from Table 2.14 and include only Planned Relative Time after Baseline.

GlaxoSmithKline  
 Example : PK01  
 Protocol : 204847  
 Population : PK

Table 3.01  

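### The planned Part 2 summaries do not separate an acute Day 15 infusion effect from change accumulated since Day 1, and the Day 15 pre-dose vital signs have no table row

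*SAP*

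**What the plan says.** **Vital signs, collection.** Protocol 7.1 (Table 5, note 2) and SAP 10.1.1 (Part 2 table, note 2) agree. For Days 1 and 15 the note begins "Vital signs will be measured within 1 hour before the start of infusion (pre-dose) and at". It then lists eight post-infusion times, the first at half an hour and the last at 12 hours. Days 2 to 14 have a reading before the morning infusion, and Day 16 has a morning reading.

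**Vital signs, reporting.** The Table 2.16 shell lists the Part 2 rows one by one. After the Day 1 times it runs "Day 2 through Day 14, Day 15 - 0.5 HR, Day 15 - 1 HR, Day 15 - 1.5 HR" and on to 12 hours, with no Day 15 pre-dose row. Table 2.17 is the matching change table, but its programming note sends the programmer to the shell of Table 2.14, which is a QTc frequency table.

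**ECG.** Note 1 schedules single ECGs at "0.5, 1, 1.5, 2, 3, 4, 6, and 12 hours after the start of infusion on Day 1 and Day 15", and single ECGs before the morning infusion on Days 2 to 14. It also states: "Triplicate 12-lead ECGs will be obtained at least 5 minutes apart within 1 hour before the start of infusion (pre-dose) on Day 1". No Day 15 pre-dose ECG is listed in either document. Protocol 7.3.5 describes pre-dose triplicates in general terms and adds no Day 15 time point.

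**Baseline.** SAP 10.3.2.1 says "the baseline value will be the latest pre-dose assessment", and its table fixes Day 1 pre-dose for both ECG and vital signs. The footnotes to Tables 2.12 and 2.15 mention the respective treatment period, but Part 2 has only one period, so they do not supply a Day 15 baseline.

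**The concern.** Vital signs and ECG belong to the Part 2 primary endpoint. Protocol 4.6.1 names blood pressure and heart rate as risks, citing excursions of 29 mm Hg and 16 beats per minute in the monkey cardiovascular study. Days 2 to 14 have only pre-infusion readings, so an infusion effect that emerges with repeat dosing can be seen only in the Day 15 profile. Telemetry runs to 48 hours post dose. If that means the Day 1 dose, as the reference in 4.6.1 to initial doses in Part 2 suggests, it leaves no continuous record on Day 15.

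A Day 15 post-infusion change measured from Day 1 has two possible sources: a response to that morning's infusion, and a shift already present before it, after 14 days of confinement and 40 earlier doses. These have different safety meanings. The planned tables report their sum, although for vital signs the reading that would split them has been taken.

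**Working it through.** **1. Schedule against table rows (Part 2; baseline counted once; screening and Day -1 left out)**

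| | Baseline | Day 1 post | Days 2-14 | Day 15 pre | Day 15 post | Day 16 | Follow-up | Total |
|---|---|---|---|---|---|---|---|---|
| Vital signs scheduled | 1 | 8 | 13 | 1 | 8 | 1 | 1 | 33 |
| Table 2.16 rows | 1 | 8 | 13 | 0 | 8 | 1 | 1 | 32 |
| ECG scheduled | 1 | 8 | 13 | 0 | 8 | 1 | 1 | 32 |
| Table 2.12 rows | 1 | 8 | 13 | 0 | 8 | 1 | 1 | 32 |

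For vital signs the one mismatch is Day 15 pre-dose. For ECG, schedule and table agree and both omit it.

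**2. What the planned change contains.** Let B be Day 1 pre-dose, P Day 15 pre-dose, and Y(t) the Day 15 value t hours after the start of infusion. Then

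Y(t) − B = [Y(t) − P] + [P − B].

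Table 2.17 would show only the left side. The first bracket is the within-day change and the second is the change accumulated since Day 1. On Day 1 the same column is already a within-day change, so the Day 1 and Day 15 rows are not the same quantity. A row for P gives the mean of each bracket if the same subjects contribute throughout. The spread of Y(t) − P still needs subject-level differences, hence a separate column.

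**3. Do the listings fill the gap?** Listings 30 and 31 cover values of potential clinical importance and subjects who have one. SAP 10.6.2 sets such limits only for blood pressure and heart rate. Protocol 9.4.1 promises that all safety data will be listed, and SAP Table 3 marks vital signs for individual listing. The Day 15 pre-dose value is therefore left out of the listings only if the narrower listing titles prevail.

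**4. Day 14 as a reference for ECG.** Day 1 to Day 15 is 14 days. With linear drift, a Day 14 reference leaves 1/14 = 7% of it, against 100% with the Day 1 baseline. Trough conditions should be alike on the two mornings. From Protocol 4.5, CL is 0.82 to 0.93 mL/min/kg and V is 0.121 L/kg. A one-compartment approximation (the protocol's own simulation model has three) gives:
- k = CL × 60/1000/V = 0.41 to 0.46 per hour
- half-life = ln 2/k = 1.7 to 1.5 h
- accumulation over 8 h = 1/(1 − exp(−8k)) = 1.04 to 1.03

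**5. What placebo can add.** Each cohort has about 8 active and 2 placebo subjects. With a common SD, the standard error of the active-placebo difference is SD × √(1/8 + 1/2) = 0.79 SD within one cohort, and SD × √(1/8 + 1/6) = 0.54 SD with placebo pooled over three cohorts.

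**The case against.** A reader might infer that an infusion effect cannot be separated from drift at all. The documents do not support that. The Day 15 pre-dose vital signs are collected, so the within-day change can be computed. For ECG, a Day 14 pre-dose reading is scheduled about 24 hours earlier at a similar trough, and the 6-hour, 12-hour and Day 16 ECGs show any return. Placebo is given as saline infusions on the same schedule, so confinement and repeated infusion are shared.

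Predicted accumulation is also only about 3 to 4%. An effect driven by concentration alone should already appear on Day 1, which has its own pre-dose readings. This stands. Day 15 matters for effects that emerge with repeat dosing, which plasma exposure does not rule out.

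A reader might also infer that change from Day 1 is the wrong or less precise contrast. It estimates total effect, cumulative plus acute, which is a legitimate safety summary. A precision ratio would need within-day and between-day SDs that the documents do not give, and would compare two different quantities. None is claimed here.

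Nor does the missing row restrict escalation decisions. Tables 2.11 to 2.17 are final-analysis deliverables, and Protocol 9.3.2 has all preliminary safety data reviewed before each escalation.

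Two limits to these answers remain. No planned analysis uses the Day 14 value as a reference, and the 10-hour fast in Protocol 6.10.1 applies to Days 1 and 15, not Day 14. Placebo is small, and by itself it does not divide a drug effect into acute and cumulative parts.

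**Conclusion.** The point holds as a gap in the planned summaries. For vital signs, one collected time point of 33 is left out, and none of the eight Day 15 post-infusion changes is shown against a same-day reference. The data exist, so this is a reporting correction. For ECG the same-day reference is absent from the schedule, and the Day 14 pre-dose ECG can largely replace it. That rests on roughly linear drift and similar troughs on the two mornings. The replacement is imperfect: it is a single ECG, whereas the Day 1 baseline averages a triplicate, and the required fast differs.

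Within-day change will still include diurnal and meal effects, so the descriptive comparison with placebo remains necessary.

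**What to change.** 1. Add a Day 15 pre-dose row to the Part 2 time points of SAP Tables 2.16 and 2.17.
2. In Table 2.17, for the eight Day 15 post-infusion times, show change from Day 15 pre-dose beside change from the Day 1 baseline. Keep the latter as the summary of total effect, and record the added reference in SAP 10.3.2.1.
3. Correct the Table 2.17 shell reference from Table 2.14 to Table 2.16.
4. In Table 2.13, for the Day 15 post-infusion times, add change from the Day 14 pre-dose ECG, with a note that it is a single reading without the Day 15 fasting requirement.
5. Optional: schedule a single Day 15 pre-dose ECG in Protocol Table 5 note 1 and add its row to Tables 2.11 to 2.13. It has to be scheduled, because SAP 10.3.3 keeps unscheduled visits out of summary tables.

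Items 1 to 4 need no new data: one row in each of two tables, one extra change column in each of two, and a corrected cross-reference. Item 5 costs one ECG per Part 2 subject, about 30 in all, in the same hour as the Day 15 pre-dose vital signs.

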**Time and Events Table: Follow-up Visit; Single and Repeat Dose Escalation (Part 1 and Part 2) and Single Dose (Part 3)**

Procedure	Follow-up Visit (7 to 10 days post last dose or early termination)
Adverse event/serious adverse event review	X
Concomitant medication review	X
Brief physical examination	X
12-lead electrocardiogram	X
Vital signs	X
Urine $\beta$ -human chorionic gonadotropin pregnancy test (women of child-bearing age)	X
Clinical chemistry, hematology, and urinalysis tests 	X

NOTE:
 
1. An aliquot of the urine sample will be collected for neutrophil gelatinase-associated lipocalin (NGAL) and kidney injury molecule 1 (KIM-1). These samples may be analyzed after the end of the study if a clinical signal is detected. Instructions for collection and storage of these urine samples are included in the Study Reference Manual. Hematology assessments will also include total iron, total iron binding capacity, ferritin, and reticulocytes. The albumin to creatinine ratio will be determined using the first morning void urine as described in protocol Section 7.3.7.
	

## 10.2. Appendix 2: Treatment States and Phases

### 10.2.1. Treatment Phases

Assessments and events will be classified according to the time of occurrence relative to dosing.

Treatment Phase	Definition
Pre-Treatment	Date < Study Treatment Start Date
On-Treatment	Study Treatment Start Date ≤ Date ≤ Study Treatment Stop Date
Post-Treatment	Date > Study Treatment Stop Date

### 10.2.2. Treatment States

Assessments and events will be classified according to time of occurrence relative to the start and/or stop date of the study treatment.

#### 10.2.2.1. Treatment States for Safety Data

Treatment State	Definition
Pre-Treatment	Date/time < Study Treatment Start Date/time
On-Treatment	Study Treatment Start Date/time ≤ Date/time ≤ Study Treatment Stop Date/time + 2 days
Post-Treatment	Date/time > Study Treatment Stop Date/time + 2 days

**NOTES:**

- If the study treatment stop date is missing then the assessment will be considered to be On-Treatment

#### 10.2.2.2. Treatment States for AE Data

Treatment State	Definition
Pre-Treatment	AE Start Date/time < Study Treatment Start Date/time
On-Treatment	If AE onset date/time is on or after treatment start date & on or before treatment stop date/time. Study Treatment Start Date/time ≤ AE Start Date/time ≤ Study Treatment Stop Date/time + 2 days
Post-Treatment	If AE onset date/time is after the treatment stop date/time. AE Start Date/time > Study Treatment Stop Date/time + 2 days
Onset Time Since 1 st Dose (Days)	If Treatment Start Date/time > AE Onset Date/time, = AE Onset Date - Treatment Start Date If Treatment Start Date/time ≤ AE Onset Date/time, = AE Onset Date - Treatment Start Date + 1 Missing otherwise.
Duration (Days)	AE Resolution Date – AE Onset Date + 1
Drug-related	If relationship is marked 'YES' on CRF OR value is missing.

**NOTES:**

- If the study treatment stop date is missing then the AE will be considered to be On-Treatment.

### 10.3. Appendix 3: Data Display Standards & Handling Conventions

#### 10.3.1. Study Treatment & Sub-group Display Descriptors

Treatment Group Descriptions				
Randomization Schedule			Data Displays for Reporting	
Part	Code	Description	Description	Order 
1	A1	Cohort A GSK3342830	GSK3342830 250 mg	1
1	A2	Cohort B GSK3342830	GSK3342830 500 mg	2
1	A3	Cohort C GSK3342830	GSK3342830 1000 mg	3
1	A4	Cohort D GSK3342830	GSK3342830 2000 mg	4
1	A5	Cohort E GSK3342830	GSK3342830 4000 mg	5
1	A6	Cohort F GSK3342830	GSK3342830 6000 mg	6
1	A7	Cohort X1 GSK3342830	GSK3342830 XXXX  mg	7
1	A8	Cohort X2 GSK3342830	GSK3342830 XXXX  mg	8
1	P	Placebo	Placebo	9
2	A9	Cohort G GSK3342830	GSK3342830 1000 mg TID	10
2	A10	Cohort H GSK3342830	GSK3342830 2000 mg TID	11
2	A11	Cohort I GSK3342830	GSK3342830 4000 mg TID	12
2	A12	Cohort Y1 GSK3342830	GSK3342830 XXXX  mg TID	13
2	A13	Cohort Y2 GSK3342830	GSK3342830 XXXX  mg TID	14
2	P	Placebo	Placebo	15
3	AJ1	Cohort J GSK3342830	GSK3342830 XXXX  mg	16
3	PJ	Placebo	Placebo	17
3	AJ2	Cohort Z1 GSK3342830	GSK3342830 XXXX  mg	18
3	PJ	Placebo	Placebo	19

#### NOTES:

- Order represents treatments being presented in TFL, as appropriate.
- Cohort X1, X2, Y1, and Y2 are created per protocol to allow 2 additional doses which may be evaluated to further understand the study drug. The Randomization Schedule does not contain the actual dose levels but instead refers to the Cohort dose level. Dose levels may change from the protocol defined levels. The TLFs will display the actual dose levels used in the study.
- The dose for Cohort X1, X2, Y1, and Y2 will be determined once the decision is made to enroll those optional cohorts.
- The dose for Cohort J will either 250, 500, 1000, 2000, 4000 or ≤6000 mg based on preliminary safety and tolerability results of doses determined to be safe and well tolerated in subjects of non-Japanese heritage after completion of the single escalation dose cohorts (Part 1).

### 10.3.2. Baseline Definition & Derivations

#### 10.3.2.1. Baseline Definitions

For all endpoints (except as noted in baseline definitions) the baseline value will be the latest pre-dose assessment.

Parameter	Study Assessments Considered As Baseline			Baseline Used in Data Display
	Screening	Day -1	Day 1 (Pre-Dose)	
Safety				
Hematology	X	X		Day -1
Clinical Chemistry	X	X		Day -1
12 Lead ECG	X	X	X	Day 1 (Pre-dose)
Vital Signs	X	X	X	Day 1 (Pre-dose)

#### NOTES :

- Unless otherwise stated, the mean of replicate assessments at any given time point will be used as the value for that time point.

#### 10.3.2.2. Derivations and Handling of Missing Baseline Data

Definition	Reporting Details
Change from Baseline	= Post-Dose Visit Value – Baseline

#### NOTES :

- Unless otherwise specified, the baseline definitions specified in Section 10.3.2.1 Baseline Definitions will be used for derivations for endpoints / parameters and indicated on summaries and listings.
- Unless otherwise stated, if baseline data is missing no derivation will be performed and will be set to missing.
- The baseline definition will be footnoted on all change from baseline displays.

### 10.3.3. Reporting Process & Standards

Reporting Process
Software

 
• The currently supported versions of SAS software [Insert Other Software as Required] will be used.
 

Analysis Datasets

 
• Analysis datasets will be created according to CDISC standards (SDTM IG Version 3.1.3 & AdaM IG Version 1.0).
 
• For creation of ADaM datasets (ADCM/ADAE), the same version of dictionary datasets will be implemented for conversion from SI to SDTM.
 

Generation of RTF Files

 
• RTF files will be generated for all reporting efforts described in the RAP.
 

Reporting Standards
General

Reporting Standards	

 
• The current GSK Integrated Data Standards Library (IDSL) will be applied for reporting, unless otherwise stated:             
 
○ 4.03 to 4.23: General Principles
 
○ 5.01 to 5.08: Principles Related to Data Listings
 
○ 6.01 to 6.11: Principles Related to Summary Tables
 
○ 7.01 to 7.13: Principles Related to Graphics
 
 
 
	
Formats	

 
• All data will be reported according to the actual treatment the subject received unless otherwise stated.
 
• GSK IDSL Statistical Principles (5.03 & 6.06.3) for decimal places (DP's) will be adopted for reporting of data based on the raw data collected.
 
• Numeric data will be reported at the precision collected on the eCRF.
 
• The reported precision from non eCRF sources will follow the IDSL statistical principles but may be adjusted to a clinically interpretable number of DP's.
 
	
Planned and Actual Time	

 
• Reporting for tables, figures and formal statistical analyses :             
 
• Planned time relative to dosing will be used in figures, summaries, statistical analyses and calculation of any derived parameters, unless otherwise stated.
 
• The impact of any major deviation from the planned assessment times and/or scheduled visit days on the analyses and interpretation of the results will be assessed as appropriate.
 
 
 
• Reporting for Data Listings:             
 
• Planned and actual time relative to study drug dosing will be shown in listings (Refer to IDSL Statistical Principle 5.05.1).
 
• Unscheduled or unplanned readings will be presented within the subject's listings.
 
• Visits outside the protocol defined time-windows (i.e. recorded as protocol deviations) will be included in listings but omitted from figures, summaries and statistical analyses.
 
 
 
	
Unscheduled Visits	

 
• Unscheduled visits will not be included in summary tables.
 
• Unscheduled visits will not be included in figures.
 
• All unscheduled visits will be included in listings.
 
	
Descriptive Summary Statistics	
Continuous Data	Refer to IDSL Statistical Principle 6.06.1
Categorical Data	N, n, frequency, %
Reporting of Pharmacokinetic Concentration Data	
Descriptive Summary Statistics	Refer to IDSL Statistical Principle 6.06.1 Assign zero to NQ values (Refer to GUI_51487 for further details)
Reporting of Pharmacokinetic Parameters	
Descriptive Summary Statistics (Log Transformed)	N, n, geometric mean, 95% CI of geometric mean, standard deviation (SD) of logged data and between geometric coefficient of variation (CV b - (%)) will be reported. $CV_b (\%) = \sqrt{(\exp(SD^2) - 1) * 100}$ (SD = SD of log transformed data)

Reporting Standards	
Parameters Not Being Log Transformed	Tmax, %AUCex, tlast, lambda_z, lambda_z_lower, lambda_z_upper, lambda_z_no. of points, Ratio of time invariance, Ratio of accumulation, Feu(t1-t2), CLr, Ae
Listings	Include all following PK parameters: Cmax, AUC0-∞, AUC0-t, AUC(0-τ), t1/2, CL, Vss, Cτ, Ratio of time invariance, Ratio of accumulation, Tmax, %AUCex, tlast, lambda_z, lambda_z_lower, lambda_z_upper, lambda_z_no. of points, Feu(t1-t2), CLr, Ae.
Graphical Displays	

 
Refer to IDSL Statistical Principals 7.01 to 7.13.
 
	

Reporting Standards
10.4. Appendix 4: Derived and Transformed Data

